#### 15.0 Data Monitoring Plan to Ensure the Safety of Participants:

We will conduct weekly interviews with the parents, asking them questions about child's behavior and functioning to collect both safety and efficacy data. The interviews will be conducted either by telephone or in person (per parental choice). Please attached interview protocol. [name], a licensed clinical psychologist will review the data. The detailed qualitative data will be collected. No statistical analysis is necessary.

If a participant shows sudden developmental regress, we will recommend immediate neurological evaluation and his/her participation will be discontinued (unless this participant has been manifesting regress prior the start of the study). If two participants suddenly manifest signs of regress (not anticipated, not seen before in prior photobiomodulation studies), we will immediately discontinue the study.

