# **Transcranial Photobiomodulation for reducing autism symptoms in children.**

*May 1, 2022*

PROTOCOL TITLE:

Transcranial photobiomodulation for reducing autism symptoms in children.

PRINCIPAL INVESTIGATOR:

Name	[name]
Department	N/A
[contact]

RESEARCHERS:

Name	[name]
Department	N/A
[contact]

Name	[name], CFA, Esq.
Department	N/A
[contact]

Name	[name]
Department	N/A
[contact]

1.0 Purpose of the study:

The purpose of this 10-week feasibility study is to assess the tolerability, safety and efficacy of Transcranial LED Therapy for language learning and reducing symptoms of autism in children.

The investigators propose to enroll up to 30 participants, 2-7 years old, all of whom have recently completed the IRB approved study by JelikaLIt. They all have been previously diagnosed with moderate to severe ASD by licensed professionals according to the Diagnostic and Statistical Manual of Mental Disorders, Fifth Edition (DSM-5) criteria for Autism Spectrum Disorder (ASD).

This will be an one-arm, open label study. Participants who were in the placebo condition in the previous study, will receive the treatment. Participants who were in the active condition in the previous study will repeat the course of treatment after the intermission of 3-6 months (depending on when they completed the study).

The hypothesis to be tested is that exposure to photobiomodulation will reduce children's symptoms of autism, as measured by the reduction of the Mean Scores of the Childhood Autism Rating Scales, compared to the initial baseline.

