**7.0 Procedures Involved:**

7.1 Location: The study will use pre-test and post-test design. The entire study on the children will be done in the office. The weekly interview with the parent may be done either in office or by phone, as preferred by the parent.

7.2 Conditions: There will be only one active condition.

7.3 Participants: The participants will be 2 to 7 years old children previously diagnosed with moderate or severe ASD. Children of all genders and races will be included in this study.

7.4 Treatment: The treatment will take place twice a week for up to 30 minutes at a time.

During the study, while participants will be wearing the photobiomodulation device, they may be playing with their parent or the experimenter, using the toys of their choice (out of the many available in the experimenter's office). The caregivers will be present during the experiment at all times. When the child and the parent arrive, they will be welcomed to the office, and introduced to the toys.

The child will be encouraged to play with toys and interact with the parent (or the experimenter).

If the child becomes uncomfortable, the parents will be able to leave the experiment without any punishment. No coercion or deception is involved in this study.

7.5 Pre and Post-Testing:

The following measurements will be used for pretest and post-test.

- Childhood Autism Rating Scale (CARS2)

CARS 2 scores will be compared for analyses.

In addition, EEG will be collected from the participants pre and post -treatment in each session. Mobile FDA cleared EEG device from Brain Scientific will be used to collect children's pre and post test EEG.

There is no known danger of EEG collecting. In this study it will be using for measuring the efficacy treatment only.

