**7.6 On-going Data Collection:** Parents will be asked to keep a daily diary of the child's behavior, specifically – words spoken, comprehension of instructions, eye contact, his sleep pattern, number of tantrums, anxiety, social interaction and eating. Qualitative data will be collected through short weekly interviews with the parents. These interviews can take place either in [name] office during the child's treatment or by phone. During those weekly interviews, the parents will be asked questions about their children's responsiveness to language, number of words they can produce, eye-contact, anxiety, frequency of tantrums, eating, and difficulties falling asleep and sleeping through the night. Please see attached proposed script for the weekly call. The qualitative data will be used to further inform and supplement quantitative data.

The study will collect qualitative and quantitative data. The quantitative data will be the total CARS2 scores of the participants, obtained before and after the study is done. Repeated-measure t-tests will be used to analyze quantitative data. In addition, we will collect Before and After Prefrontal cortex EEG from the control and experimental treatment groups to measure electrophysiological changes in Prefrontal cortex. after treatment. EEG data will be analyzed (using Time-Frequency analysis), and after baseline normalization, the data will be used in aggregate to compare conditions numerically. In addition, we will obtain qualitative data from weekly parental interviews, during which we will ask participants' parents about their children's behavior (see attached protocol). Qualitative data will be used for information purposes and will supplement quantitative data.

The PI will analyze quantitative and qualitative data. An independent contractor (a neuroscientist) will be analyzing the collected EEG data at the end of the study, however, the individuals conducting the analysis will not have access to the private identifiable information.

**7.8 Confidentiality:** Participants' confidentiality will be protected by assigning them Study ID. The quantitative data will be analyzed and reported only as aggregate (averages and F scores). The qualitative data will be studied only by the researchers and, if reported for illustrative purposes only, it will be attached to the Study ID (not the identifying information). The participants will be asked for consent to report qualitative data with the Study ID.

●

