### 13.0 Risks to Participants:

Potential Risks	Mitigating Factors
Some questions may be very personal or upsetting to the parents	Parents may skip any questions that they do not want to answer.
The child may feel uncomfortable wearing the headband and may want to take it off early	
If the child wants to take off the headband, we will first encourage him to wear it, by attempting to divert his attention to other things, such as toys and music.
 
If, however, the child insists on taking off the headband, he / she will not be forced to wear it and he / she may be able to take it off before the conclusion of the session.

Breach of confidentiality (child's data being seen by someone who shouldn't have access to it)	We'll keep all children identifying information separate from the research data, but we'll be able to link it by using a study ID. We will destroy this link after we finish collecting and analyzing the data.
The child maybe receiving concomitant medical treatment	Even though there are no interaction of the tPBM with any medications, children currently receiving any psychotropic medications on a regular basis, will be excluded from participating in this pilot-study. This will be determined during initial screening.
The child might be receiving behavioral Intervention such as ABA simultaneously with participating in the study.	
There is no known negative interaction of this treatment with any behavioral treatment.
 
The children should be able to receive their regular behavioral therapies while being enrolled in this study.
 
Clinicians will monitor (based on parental and therapists' interviews) each child's progress.

There may be risks that we do not know about yet. Exposure to LED lights is not known to have any negative side effects.	
After years of study, there are no known negative side effects of photobiomodulation.
 
Throughout the study, we'll tell parents if we learn anything that might affect their decision to let their child participate.
 
Minor transient side effects may include headaches, agitation, and hyper-activity. These side effects are sometimes observed in the beginning of the treatment and usually resolve on their own. Parents will be informed of these potential minor side-effects in the Consent form.

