Some participants may have to be withdrawn from the study	If the child is not able to attend all the required sessions and the caregiver is not able to reschedule a cancelled session within a 7-day window, then the child may have to be withdrawn from the study.

	
 
1. If the child has completed at least 8 weeks, we will ask them to do final assessments and this data will be included in the final analysis.
 
2. If the child has completed less than 8 weeks and missed a week due to sickness, the family will be offered to restart the 12-week course. Regardless of the outcome, we will ask the child's parents for permission to contact them in the future with follow up questions regarding the child's behavior.
 

--	-------------------------------------------------------------------------------------------------------------------------------------------------------------------------------------------------------------------------------------------------------------------------------------------------------------------------------------------------------------------------------------------------------------------------------------------------------------------------------------------------------------------------

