#### 14.0 Provisions to Protect the Privacy and Confidentiality of Participants and the Research Data:

Participants will be only interacting with [name], [name], Esq, or [name] (researcher). Participants and their parents will be tested individually, in a quiet room, and their confidentiality will be protected, as they won't be interacting with each other or with anybody else outside of the researchers.

The participants will be explained that they can refuse to answer any question. They can also refuse to participate in the study at any time. We do not anticipate uncomfortable questions, however, we will assure the participants that their level of comfort is of utmost importance, and we will explain to them that there is no penalty involved for their refusal to answer any specific question.

Only [name] and [name] will be able to access individual information. The participants will be immediately assigned Study ID number and only STUDY ID will be used for data analysis and reporting. Only aggregated data will be used for further reporting to the scientific community or to the business community. Individual data will be reported for illustrative purposes only with STUDY ID (not identifying personal information).

The following information will be included as data: Signed consent form (immediately scanned and stored in a cloud). Pre and Post-test Cars2 scores (with STUDY ID assigned). Weekly interview data (with STUDY ID assigned).

Identifying information will include Name and Age, Gender and number of therapy hours of the participant, Name and phone number of the parent. Children's age, gender and number of therapy hours will be used for matching purposes (for assigning to the control or treatment condition). Neither names of the participants nor names and phone numbers of their parents will be used for data analysis or reporting. Their names and phone numbers will be stored separately, in encrypted (password protected) file, in a secure cloud. Secure clouds as well as encryption and password protection will be used to protect identifying information.

The raw research data will be stored for 6 years. The identifying parental information will be kept for a year, for potential follow up interviews. The consent form will include their permission to keep identifying data for a year.

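### Safety and tolerability are stated aims, but the visible plan specifies no count of side effects, early headband removals or withdrawals; a short descriptive plan would supply them

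*Protocol*

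**What the plan says.** Protocol section 1.0 gives the purpose of this 10-week feasibility study as "to assess the tolerability, safety and efficacy of Transcranial LED Therapy" for language learning and autism symptoms. Section 2.3 restates the aim in terms of the product's safety and comfort.

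Section 15.0 collects safety information through weekly parent interviews, reviewed by a psychologist, and then says: "The detailed qualitative data will be collected. No statistical analysis is necessary". It does hold one numeric safety rule: unexpected developmental regression ends that child's participation, and a second such child stops the study.

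Section 7.6 defines the numerical data: "The quantitative data will be the total CARS2 scores of the participants, obtained before and after the study is done", with EEG added. The interview covers response to language and "number of words they can produce, eye-contact, anxiety, frequency of tantrums, eating, and difficulties falling asleep and sleeping through the night"; the daily diary covers similar ground. Section 14.0 lists the study data as the consent form, then "Pre and Post-test Cars2 scores (with STUDY ID assigned). Weekly interview data (with STUDY ID assigned". Sections 14.0 and 17.0 say that results will be reported in aggregate, with individual data used only as illustration.

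Section 9.0 names tiredness and headache as uncommon effects in first-time users. Section 13.0 names headache, agitation and hyper-activity, early in treatment. Section 13.0 also foresees that "The child may feel uncomfortable wearing the headband and may want to take it off early", and that if sessions are missed and not rescheduled, "then the child may have to be withdrawn from the study".

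**The concern.** A feasibility study that sets out to assess tolerability should be able to say how many children had a problem, out of how many, and how often the device came off early. The visible plan does not arrange for this. The only sentence on analysing the safety interviews declines statistical analysis, and none of the four named side effects appears among the listed interview or diary topics, although sleep, anxiety and tantrums may overlap with them.

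Headband removal matters most in practice. It is the tolerability event that the protocol itself foresees, it happens in front of study staff, and if nobody writes it down it cannot be recovered later.

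The denominator also needs care. Under section 1.0 the arm mixes children receiving active treatment for the first time with children repeating a course after 3 to 6 months. A later statement about the whole arm could be read as first-use evidence from about twice as many children as this study can supply.

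**Working it through.** **1. Inputs.** Section 2.4 gives the earlier trial's groups as 16 active and 14 sham. Section 4.0 admits only children from that trial, and section 5.0 sets the maximum at 30. Check: 16 + 14 = 30, which agrees. So this study can have at most 14 first-time and 16 repeat users. Both are ceilings, since families may decline and children are re-screened. The protocol gives no precision figure for safety to reproduce.

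**2. Tracing each item through the visible text.**

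| Item | Where foreseen | Recording planned | Count planned |
|---|---|---|---|
| Tiredness, headache | 9.0; 13.0 (headache) | Not among the topics in 7.6 | No |
| Agitation, hyper-activity | 13.0 | Not named in 7.6; may overlap with tantrums and anxiety | No |
| Early headband removal | 13.0 | No | No |
| Withdrawal, restart | 13.0 | Handling described | No |

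**3. Precision if counts were made.** For zero events in n children, the two-sided exact (Clopper-Pearson) 95% upper limit is 1 − 0.025^(1/n):

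- n = 14 (first-time): 23.2%
- n = 16 (repeat): 20.6%
- n = 30 (whole arm): 11.6%
- n = 7 (assumed: half the former-sham children return): 41.0%

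The ratio for 0/14 against 0/30 is 23.2 / 11.6 = 2.0.

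For x events, the limits are the 2.5% quantile of Beta(x, n − x + 1) and the 97.5% quantile of Beta(x + 1, n − x). One event gives 1/14 = 7.1% (0.2% to 33.9%) and 1/30 = 3.3% (0.1% to 17.2%).

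**4. What such a table can detect.** The chance of seeing no event is (1 − r)^n. The documents give no event risk, so r is assumed over a range:

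| Assumed true risk r | n = 14 | n = 30 |
|---|---|---|
| 1% | 87% | 74% |
| 5% | 49% | 21% |
| 10% | 23% | 4% |
| 20% | 4% | 0.1% |

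The table would inform about common events and say little about rare ones with either denominator.

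**5. Unit for headband removal.** Two sessions a week (section 7.4) for 10 weeks (section 1.0) makes 2 × 10 = 20 sessions per child. A count of children with any removal treats one removal in 20 like 20 in 20, so sessions per child are needed. A planned wearing time is needed too: section 2.3 gives about 5 to 10 minutes, and section 7.4 up to 30.

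**The case against.** The strongest reply is that section 15.0 is about monitoring: who looks at the data and when to stop. Declining statistical analysis there is reasonable, and nothing forbids a simple count. That is fair, but no other visible section takes up the task.

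Several stronger readings are tempting and not supported:

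- A reader might infer that safety can be reported only as narrative. Sections 14.0 and 17.0 commit to aggregate reporting, and interview data are held by study ID. What is missing is a specification of what will be aggregated.
- A reader might infer that a misleading pooled rate is planned. None is. The factor of two in the upper limit concerns a statement someone might make later.
- A reader might infer that all side effects belong to first-time users. Section 9.0 says so only for tiredness and headache. Section 13.0 ties headache, agitation and hyper-activity to the start of treatment, which could equally be the start of a second course. Nothing links headband removal or withdrawal to earlier exposure.
- A reader might infer that only 14 children can ever inform first use. The 16 former-active children had their first course in the earlier trial; its side-effect data are simply not shown.
- A reader might infer that children go unmonitored. The weekly review and the two-child stopping rule stand.

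Absence can be asserted only for the text available here. The interview script is an attachment that is not shown, section 6.0 is not visible, and part of the SAP is missing. The visible SAP text reports CARS results from the active-versus-sham comparison, so its silence on safety says little about this study.

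It is also right that bare counts would be hard to interpret. Agitation and hyper-activity may precede treatment in these children, there is no control group, and withdrawal needs a rule because section 13.0 lets some children restart. These points shape the fix; they do not remove the need for it.

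**Conclusion.** The point holds as a modest, optional improvement. In the visible text, two stated aims have no specified counts, denominators or precision, and early headband removal is not planned to be recorded at all. Counts with exact intervals would serve those aims better than leaving the analysis unspecified.

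The size is limited. With full return and no events, this study could exclude a first-use risk above 23.2% (0/14), against 11.6% for the whole arm (0/30). No document sets a safety threshold that either figure would cross. The result rests on the 14 and 16 being ceilings, on the assumed event risks in the working, and on the unseen script and sections not already containing such a plan. The split by earlier exposure is descriptive and rests on section 9.0 for tiredness and headache only. The CARS analysis is not touched.

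**What to change.** In section 15.0, replace the sentence that declines statistical analysis with a descriptive plan along these lines:

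> We will report (a) the number of children with tiredness, headache, agitation or hyper-activity, each separately, that is new or worse than before the first session; (b) for each child, the sessions completed and the sessions in which the headband came off before the planned time; (c) the number of children withdrawn, with those who restart the course listed separately. Each is given with its denominator, and proportions of children with an exact two-sided 95% interval. Results are shown for the whole arm and, descriptively, for former-sham and former-active children. Statements from this study about first-time use will use the former-sham denominator.

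Three practical steps go with it. Ask about the four effects before the first session and, if the script does not already do so, in the weekly call. State the planned wearing time per session. Have staff note headband wear each time; this is feasible because "The entire study on the children will be done in the office". First-use data from the earlier trial may be shown alongside if they exist and are labelled as such.

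The cost is a short paragraph, one table, up to four questions in an existing call, a brief pre-treatment check and one line per session, with no new visits. The downsides are slightly longer calls, wide intervals that say little about rare events, prompted questions that may raise reporting relative to the earlier trial, and no control group to separate background from treatment effects.

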## 2.3 Background of the Cognilum Physical Device:

We are developing a safe and effective protocol for administering tPBM via a wearable device. This physical device is getting developed by JelikaLite Corp. The parameters are developed by [name] (the researcher of this study), [name] (leading photobiomodulation expert from Harvard Medical School and an advisor to JelikaLite), [name] (leading neuroscientist who is studying photobiomodulation at Boston Medical University and an advisor to JelikaLite), and [name] (an industrial product designer with over 30 years of expertise in designing medical devices). The purpose of this feasibility study is to evaluate the safety and comfort of the product, as well as preliminary efficacy of the treatment effect. The device will stimulate Default Mode Network (to increase brain connectiveness) as well as Broca and Wernike areas (to facilitate speech comprehension and production) and Occipital lobe (as many ASD children rely on visual information for language learning). The device is physically light, comfortable to wear for children and could eventually be used at home as frequently as necessary.

The reason why the device may be helpful to children is because of the science of photobiomodulation. The device will have embedded LED lights in it, which will shine red light and near infra red lights. The children will wear the device for approximately 5-10 minutes, twice a week (closely replicating the protocol of Leisman et al as well as the clinical study at MGH). The light stimulates mitochondrial ATP production. Only about 2% of the light penetrates the skull. However, because brain is the largest energy consuming organ of the body, even those 2% result in significant improvement of the symptoms (even small boost in ATP production results in significant improvement). Having more energy enables the brain cells to heal, grow and form new neural connections. Other benefits of tPBM is increased blood flow to the brain, which increase brain oxygen supply and reduce inflammation.

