### Rationale for the device:

*Safety of Photobiomodulation:* Photobiomodulation has been extensively studied on humans for more than 30 years, including its use for neurological conditions. There are several photobiomodulation products (for neurological conditions) that are on currently on the market (using both LED and Lasers). The consumers report no side-effects.

After more than three decades of research there are no known major side effects attached to photobiomodulation therapy.

The device has been designated as "Non-Significant Risk" by the FDA.

*Rare Minor Side effects for first time users only include:* Tiredness (temporary) – probably due to the release of metabolites but the majority report a resurgence of energy. Headaches (temporary) – from the reactivation of neural connections and increased microcirculation.

*Safety Issues of our product specifically:* Our product emits non-laser based irradiation (incoherent light) with a low level energy intensity. Infrared emits non-laser based irradiation (incoherent light) with a low level energy intensity. We use 850 nm. The participants might perceive slight warmth. No other perceptions will be produced by wearing the device. No feelings of discomfort are anticipated (the device is especially made for children, it's very comfortable and soothing to wear). There are no known side-effects of photobiomodulation (with 30 years of research and studies, including research on 5 year old children diagnosed with ASD).

Rationale for the study:

The study activities include: 1) wearing the device and / or 2) free play. In addition, the parents will be interviewed about the child's behavior on a weekly basis.

None of these activities present greater than minimal risk to the health and well-being of the participants.

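### Tolerability and safety are stated aims, but the plan provides no count or rate for either

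*Protocol*

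**What the plan says.** **Aims.** Section 1.0 of the protocol says the study will "assess the tolerability, safety and efficacy of Transcranial LED Therapy". Section 2.3 restates this: "The purpose of this feasibility study is to evaluate the safety and comfort of the product", with preliminary efficacy mentioned after it.

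**Safety data and their handling.** Section 15.0 takes safety data from the weekly parent interview and has a licensed clinical psychologist review them. It describes the data as qualitative and adds: "No statistical analysis is necessary". The same section has rules for discontinuing a participant, and the study, for sudden developmental regress.

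**What is asked.** Section 7.6 lists the interview topics as "responsiveness to language, number of words they can produce, eye-contact, anxiety, frequency of tantrums, eating, and difficulties falling asleep and sleeping through the night". The daily diary has similar topics. Sections 7.6 and 15.0 both refer to an attached interview script or protocol.

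**What is foreseen.** Section 13.0 states: "Minor transient side effects may include headaches, agitation, and hyper-activity". The device rationale in section 9.0 names temporary tiredness and headaches, and also says: "There are no known side-effects of photobiomodulation". Section 13.0 expects that some children will want the headband off; a child who insists is not forced: "he / she may be able to take it off before the conclusion of the session".

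**What is analysed.** Sections 7.5 and 7.6 plan analyses of CARS2 scores and EEG. The SAP text covers CARS only.

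**The concern.** Two of the three aims have no planned result. Section 15.0 does more than leave a detail out: it says that the safety data need no statistical treatment, and nothing elsewhere supplies a summary in its place. The study could therefore end without saying how many children had a headache or became agitated, or how often a session was cut short.

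Any bias is likely to be in one direction. If a symptom is not asked about, a parent may not mention it, and many of these children may be unable to report it themselves. Section 9.0 already asserts an absence of side effects next to its own list of them. Without a count and a denominator, a lack of complaints could be reported as confirmation. Sections 14.0 and 17.0 restrict scientific reporting to aggregated data, with individual accounts as illustration only, so safety material that is never aggregated would reach readers mainly as anecdote.

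**Working it through.** The plan gives no safety rate, precision target or basis for the sample size, so there is no figure to reproduce. The check has two parts.

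**1. Each aim against its data and its summary**

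| Aim | Data specified | Summary specified |
|---|---|---|
| Efficacy | CARS2 before and after; EEG (7.5, 7.6) | t-tests; EEG comparison (7.6; SAP, Primary Analyses) |
| Safety | Weekly parent interview (15.0) | Qualitative review; regress rules; no statistical analysis (15.0) |
| Tolerability or comfort | Early removal foreseen (13.0); no record of it specified | None |

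The side effects against the listed topics in section 7.6:

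- Headache (9.0 and 13.0): not listed, and no near equivalent.
- Tiredness (9.0): not listed; sleep overlaps in part.
- Agitation (13.0): not listed; anxiety and tantrums overlap in part.
- Hyperactivity (13.0): not listed.

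Anxiety, tantrums and sleep also serve as efficacy topics. The data inventory in section 14.0 names consent forms, CARS2 scores and interview data, with no adverse event or session record.

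**2. What a descriptive summary would deliver**

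Inputs: n = 30, the maximum in section 5.0; former arm sizes of 16 active and 14 sham, from section 2.4. True event rates are assumptions.

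For zero events in n children, the exact (Clopper-Pearson) two-sided 95% upper limit is 1 − 0.025^(1/n):

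- n = 30: 1 − 0.025^(1/30) = 11.6%
- n = 25: 13.7%
- n = 20: 16.8%
- n = 16: 20.6%
- n = 14: 23.2%

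For x events in 30, the limits are the 2.5% quantile of Beta(x, 31 − x) and the 97.5% quantile of Beta(x + 1, 30 − x):

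- 1 event: 0.1% to 17.2%
- 3 events: 2.1% to 26.5%
- 6 events: 7.7% to 38.6%

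The chance that at least one of 30 children has an event of true rate p is 1 − (1 − p)^30:

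- p = 1%: 26%
- p = 5%: 1 − 0.95^30 = 79%
- p = 10%: 96%

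So an effect with a true rate of 5% or more would probably occur at least once in a full study. It enters the results only if someone asks about it and counts it.

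**The case against.** **The sentence may concern monitoring only.** It stands in a data monitoring plan, between the psychologist's review and the stopping rules, and can be read as saying that ongoing surveillance needs no statistical testing. That is a fair reading, and on it final counts are not forbidden. It does not rescue the plan, because no other available section supplies a safety or tolerability summary.

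**A reader might infer that the plan rules out all safety analysis.** It does not. A psychologist reviews the interviews, and there are rules for regress. What is missing is narrower: neither provision produces an event rate, and the rules cover regress alone.

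**A reader might infer that the interviews are unstructured, or that they leave out the named side effects.** The documents do not support this. The interviews follow a script, which was not available and may contain these questions. Only the listed topics can be said not to name them.

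**Other sources exist.** Parents keep a daily diary, caregivers attend sessions, and section 13.0 has clinicians follow progress through parent and therapist interviews. These may bring events to light, but no count from them is planned.

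**A reader might take the minor effects to be confined to first-time users, which would make a split by former arm essential.** Only section 9.0 says this, for tiredness and headache. Section 13.0 places headache, agitation and hyperactivity early in treatment without that restriction. The split is therefore optional.

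**A feasibility study of this size needs no safety test.** Agreed; counts with intervals are enough.

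**Conclusion.** The point holds in this form: tolerability and safety are aims, and the available plan specifies no count, percentage or interval for side effects or for early device removal. The listed topics do not name four effects that the protocol foresees, with partial overlap for some of them.

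The size of the matter is the difference between no estimate and a modest one. With all 30 children enrolled and no events of a given kind, the data would be compatible with a true rate of up to 11.6%; with fewer children the limit is wider. The limits of 20.6% and 23.2% by former arm assume that every child from the earlier study returns, whereas section 5.0 says only up to 30 and section 8.0 requires re-screening.

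The plan should be changed. Confidence is medium: the interview script, the protocol text between sections 5.0 and 7.0, and the SAP text before its data collection and analysis section were not available, and an endpoint list or side-effect questions there cannot be excluded. An endpoint list would still have to be reconciled with section 15.0.

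**What to change.** Replace the sentence in section 15.0 with a descriptive rule:

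1. At every weekly interview, ask about headache, tiredness, agitation and hyperactivity, unless the script already does so.
2. Log each session that is refused or ended early.
3. Report the number and percentage of children with each event, and the percentage of sessions ended early.
4. Give exact 95% confidence intervals for the proportions of children, and show the upper limit when the count is zero. Do not apply a simple binomial interval to sessions, since sessions from one child are not independent.
5. Optionally, repeat the table by former arm.

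Before a session can be classed as ended early, sections 2.3 and 7.4 must be reconciled: the first gives about 5 to 10 minutes of wear, the second up to 30 minutes per treatment.

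The cost is a few fixed questions in an interview already held, one field in a session log and one table. Treatment, sample size and the regress rules are untouched. The downside for the sponsor is a safety statement less favourable than an absence of side effects.
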